4.0 Recruitment Methods

4.1 Identification of subjects

Potential subjects will be identified within our Minimally Invasive Gynecologic Division Outpatient clinic location or new patients referred by other physicians from other OBGYN clinics. No additional recruitment materials will be used; we have in place a system of referrals to our division for endometriosis patients from which we will pre-screen patients. We will utilize Study Finder. We will also register this study at ClinicalTrials.gov.

4.2 Recruitment process

Subjects will be recruited by various means as listed above, but primarily from the Minimally Invasive Gynecologic Division Outpatient Clinic. We will approach the potential subjects in person and/or via telephone contact and she will be given an introduction to the study. Participation will be entirely voluntary and will in no way affect her clinical care. We will ask permission to collect and share contact information with the study coordinator to assist with contacting patients for screening, recruitment, follow up visits and completing surveys.

4.2.1 How potential subjects will be recruited.

After identifying potential subjects, the study coordinator will contact the potential subject and further explain the study to them to assess eligibility and provide more information (i.e. consent document) if further eligible. Potential subject may also be a self-referral.

We do not anticipate having any difficulty recruiting these women into the study as we are currently one of the highest volume Minimally Invasive Gynecologic Surgery (MIGS) groups in the region. In 2016, we had 2700 patient encounters for endometriosis/female pelvic pain. As of August 2019, we have added two additional providers to our MIGS group.

The PI will monitor recruitment and retention rates for the study monthly to ensure that the goals are being met. In addition, we have collaborated with the Penn State Clinical Trials Office and Office of Marketing and Communications to promote the study and increase recruitment efforts. IRB approved flyers will be hung in our Minimally Invasive GYN Surgery and around campus at approved locations. An approved online ad will be posted on public endometriosis groups.

Visitors can browse by topic or search for a keyword to discover available studies at Penn State Hershey Medical CenterWe will also register this study at ClinicalTrials.gov. If recruitment and retention are inadequate, we will use IRB approved recruitment materials to begin to advertise in the broader central Pennsylvania area and with offices known to refer endometriosis patients to our practice.

4.2.2 Where potential subjects will be recruited.

Subjects will be recruited from the Hope Drive clinic location at the Pennsylvania State University Hershey Campus, other OBGYN clinics or as a self-referral.

4.2.3 When potential subjects will be recruited.

Potential subjects will be approached during their routine clinic visit or self-referral. Once identified as a possible participant, we will offer more information and ask permission to provide their contact information to the study coordinator. From there, the study coordinator will reach out.

4.2.4 Describe the eligibility screening process and indicate whether the screening process will occur before or after obtaining informed consent.

When the study coordinator receives the name of a potential subject, a call is made to assess eligibility using the IRB approved phone script. If excluded, the phone interview is stopped at that time. If eligible the subject is scheduled for a visit. A HIPAA waiver is being requested for the purposes of pre-screening procedures (i.e. medical record review, if applicable) and verbal consent to keep contact information for future research purposes. Written informed consent will be obtained prior to enrollment into the study.

5.0 Consent Process and Documentation

5.1 Consent Process:

Check all applicable boxes below:

X Informed consent will be sought and documented with a written consent form [Complete Sections 5.2 and 5.6]

X Implied or verbal consent will be obtained – subjects will not sign a consent form (waiver of written documentation of consent) [Complete Sections 5.2, 5.3 and 5.6]

Informed consent will be sought but some of the elements of informed consent will be omitted or altered (e.g., deception). [Complete section 5.2, 5.4 and 5.6]

Informed consent will not be obtained – request to completely waive the informed consent requirement. *[Complete Section 5.5]*

5.2 Obtaining Informed Consent

5.2.1 Timing and Location of Consent

In according to HRP-090 SOP for the Informed Consent Process, the potential subject will be given a copy of the most current approved consent document for review in advance. The consent process will take place in a private room setting in the Clinical Research Center (CRC) during Visit 1 – Screening Visit. The consent document will be provided for review and discussion. Consent will be obtained prior to any study procedures being done.

5.2.2 Coercion or Undue Influence during Consent

The subject will be informed that their participation in the study is entirely voluntary. The subject will receive a copy of the consent form to read at home prior to making an enrollment appointment. At the time of consent, all sections of the informed consent will be thoroughly reviewed with the subject and all of the subject's questions will be answered prior to signing. A copy of the signed consent form is provided to the subject.

5.3 Waiver of Written Documentation of Consent

5.3.1 Indicate which of the following conditions applies to this research:

The research presents no more that minimal risk of harm to subjects and involves no procedures for which written consent is normally required outside of the research context.

The only record linking the subject and the research would be the consent document and the principal risk would be potential harm resulting from a breach of confidentiality. Each subject will be asked whether the subject wants documentation linking the subject with the research, and the subject's wishes will govern. (*Note: This condition is not applicable for FDA-regulated research. If this category is chosen, include copies of a consent form and /or parental permission form for participants who want written documentation linking them to the research.*)

OR

If the subjects or legally authorized representatives are members of a distinct cultural group or community in which signing forms is not the norm, that the research presents no more than minimal risk of harm to subjects and provided there is an appropriate alternative mechanism for documenting that informed consent was obtained. (*Note: This condition is not applicable for FDA-regulated research.*)

Describe the alternative mechanism for documenting that informed consent was obtained:

Informed consent will be obtained at Visit 1. Please see 5.3.2.

5.3.2 Indicate what materials, if any, will be used to inform potential subjects about the research (e.g., a letter accompanying a questionnaire, verbal script, implied consent form, or summary explanation of the research)

A waiver of the consent process is requested for recruitment purposes in pre-screening the medical record to identify eligible subjects for the study from our clinic population. We would like to ensure that the subject is 18 -45 years old, not currently pregnant, and has a diagnosis of endometriosis. Once we have determined these baseline characteristics, we will be using the CBD Phone Screening Transcript unloaded in the recruitment materials to further screen patients prior to an in-person Screening Encounter (Visit 1). We will obtain verbal authorization

at the time of the pre-screening phone encounter or in patient clinic visit, but written Informed consent will be obtained at the Screening Encounter.

- 5.4 Informed consent will be sought but some of the elements of informed consent will be omitted or altered (e.g., deception). N/A
- 5.5 Informed consent will not be obtained request to completely waive the informed consent requirement. N/A

5.6 Consent – Other Considerations

5.6.1 Non-English-Speaking Subjects

Not applicable. Subjects who do not speak English will not be enrolled as the consents and surveys will be conducted in English and would require the ability to read and speak English.

- 5.6.2 Cognitively Impaired Adults
 - 5.6.2.1 Capability of Providing Consent N/A
 - 5.6.2.2 Adults Unable to Consent N/A
 - 5.6.2.3 Assent of Adults Unable to Consent N/A
- 5.6.3 Subjects who are not yet adults (infants, children, teenagers)
 - 5.6.3.1 Parental Permission N/A
 - 5.6.3.2 Assent of subjects who are not yet adults N/A
- 6.0 HIPAA Research Authorization and/or Waiver or Alteration of Authorization
 - 6.1 Authorization and/or Waiver or Alteration of Authorization for the Uses and Disclosures of PHI

Check all that apply:

CHECK	an that apply.
	Not applicable, no identifiable protected health information (PHI) is accessed, used or disclosed in this study. [Mark all parts of sections 6.2 and 6.2 as not applicable]
	disclosed in this study. [Wark an parts of sections 6.2 and 6.5 as not applicable]
X	Authorization will be obtained and documented as part of the consent process. [If this is the only box checked, mark sections 6.2 and 6.3 as not applicable]
X	Partial waiver is requested for recruitment purposes only (Check this box if patients' medical records will be accessed to determine eligibility before consent/authorization has been obtained). [Complete all parts of sections 6.2 and 6.3]
	Full waiver is requested for entire research study (e.g., medical record review studies). [Complete all parts of sections 6.2 and 6.3]
Χ	Alteration is requested to waive requirement for written documentation of authorization (verbal authorization will be obtained). [Complete all parts of sections 6.2 and 6.3]

6.2 Waiver or Alteration of Authorization for the Uses and Disclosures of PHI

6.2.1 Access, use or disclosure of PHI representing no more than a minimal risk to the privacy of the individual

6.2.1.1 Plan to protect PHI from improper use or disclosure

Information is included in the "Confidentiality, Privacy and Data Management" section of this protocol.

6.2.1.2 Plan to destroy identifiers or a justification for retaining identifiers Subjects who are identified through review of PHI will be contacted and offered information about the study. If they are not interested, we will not keep any of their PHI on any paper or electronic screening logs, they will only be identified by initials and date they were contacted. Those who do agree to participate will have their PHI retained as described for this study.

6.2.2 Explanation for why the research could not practicably be conducted without access to and use of PHI

The protocol has strict and specific inclusion/exclusion criteria for subjects to qualify. Access to PHI in the medical record of a potential subject is necessary to assess eligibility prior to giving study information and the consent process. Discussion about the research will take place only if the patient appears to be eligible based on pre-screening efforts.

6.2.3 Explanation for why the research could not practicably be conducted without the waiver or alteration of authorization

The waiver is requested during pre-screening efforts and pre-enrollment to assess and identify only those women potentially eligible as well as the ability of the patient to be compliant.

6.3 Waiver or alteration of authorization statements of agreement

Protected health information obtained as part of this research will not be reused or disclosed to any other person or entity, except as required by law, for authorized oversight of the research study, or for other permitted uses and disclosures according to federal regulations.

The research team will collect only information essential to the study and in accord with the 'Minimum Necessary' standard (information reasonably necessary to accomplish the objectives of the research) per federal regulations.

Access to the information will be limited, to the greatest extent possible, within the research team. All disclosures or releases of identifiable information granted under this waiver will be accounted for and documented.

7.0 Study Design and Procedures

7.1 Study Design

We propose to conduct a randomized double–blind placebo-controlled pilot study to evaluate the effectiveness of cannabidiol on the management of endometriosis-related pain.

Potential subjects will be pre-screened in the Penn State Minimally Invasive GYN Surgery Clinic for moderate to severe endometriosis associated pain (VAS > 3). Subjects will be pre-screened from new and existing patients receiving care from the MIGs division of OBGYN for the diagnosis of endometriosis. Those meeting all inclusion and exclusion criteria who are willing to participate will receive a detailed history and physical exam, appropriate bloodwork and undergo informed consented at the Screening Visit. Baseline survey data will be collected and entered into the RedCap secured database. At this time,

Page 14 of 37 (V.01/21/2019)

subjects will be set up to receive automated links via email to complete daily diary entries (including VAS scores) directly into RedCap.

After the screening visit, the subjects will be scheduled to have a 1-2 week follow-up for the enrollment visit. During that week, the patient's will be asked to complete their daily electronic diaries and screened for daily reporting adherence. Subjects having completed 5 or fewer daily diary entries during this baseline collection period will be informed of the exclusion from enrollment without at least 80% adherence to the daily diary entries and offered one additional 7-day period to improve adherence. If at the conclusion of the second 7 day run in period of gathering baseline daily diary entries, they continue to have < 80% adherence, they will be considered a screen failure and withdrawn from the study.

Randomized subjects will receive either (1) placebo (2) low dose CBD (3) high dose CBD. This study will include an 8-week intervention period during which subjects will be asked to record daily electronic VAS scores, pain medication use and a number of other parameters. They will return at week 12 for a 4 - week post-treatment visit, where they can also choose to enroll in an optional pharmacokinetic study. Participants will complete the Endometriosis Health Profile-30 (EHP-30), Patient Global Assessments (PGAs), and, if partnered and sexually active, the Female Sexual Function Index (FSFI) surveys at 0, 4 and 8, 12 weeks as well as the Patient Global Impression of Change (PGIC) surveys at 4, 8, and 12 weeks. Patients will also have bloodwork done at weeks 0, 4, 8, 12 to assess for circulating markers of inflammation. At week 8, this bloodwork will include circulating CBD levels to assess for steady state concentrations. We will perform bloodwork to assess for possible side effects e.g. liver dysfunction throughout the study duration. Please refer to Section 7.2 Study Procedures for timing and test.

Subjects will be screened for side effects and asked to record pain medication use throughout the duration of the study. At each visit, subjects will be dispensed a 4 week supply of medication **(NETA and CBD)** from the Investigational Pharmacy. They will be required to bring medication bottles to each visit to verify drug accountability. Oxycodone (if prescribed) and NETA pills will be counted and recorded. Additional refills will be provided as needed. The study drug bottle will be inspected and returned to the clinician. The patient will be provided with a new supply of study drug at Visit 3. All NETA and study drug will be returned at the completion of the study.

At the completion of the study, all subjects will be offered the opportunity to do pharmacokinetic testing with sublingual CBD until a maximum number of 4 patients are enrolled. We plan for a total of 3-4 patients. This will be entirely voluntary and they will be compensated appropriately for their time. The testing will include 24 hours of monitoring with sequential blood draws to determine the pharmacokinetic parameters of sublingual CBD after administration and one salivary pH. They will be discharged at 24 hours and asked to return to the clinic at 48 hours for one final lab draw. We will stop recruitment once we have achieved the desired number of participants.

Procedure	Prescreen	Visit 1 -	Visit 2 -	Visit 3 –	Visit 4 –	Visit 5 -Week 12
		Screening	Enrollment	4 weeks	8 weeks	(4 weeks post
		Encounter	Visit, 0	(+/- 3	(+/- 3	treatment, +/- 3
			weeks	days)	days)	days)
Screening Criteria	X					
Informed Consent		X				
Detailed History &		X				
Physical Examination						
Physical Assessment			X	X	X	X
(Review of systems,						

7.2 Study Procedures

adverse events,					
Medication Review)					
Urine Toxicology	Х				X
Urine Pregnancy Test	Х				X
LFTs	Х		X	X	X
CBC, BMP	Х			X	
Inflammatory Markers		X	X	X	X
PK (Steady State)				X	
Survey: C-SSRS	Х		X	X	X
Survey: WERF	Х				
Survey: EHP-30, PGA,		X	X	X	X
FSFI					
Survey: PGIC			X	X	Х
Study Drug Dispensed		X	X		
Drug Reconciliation			X	X	
Daily Pain Scores	X	X	X	X	

Some of these visits may be done remotely via tele-health, HIPAA compliant conferencing or phone for various reasons, some of which may include the subject unexpectedly cannot make it to the research center, she lives and/or moves a significant distance away from the research center and wants to continue participation and/or there are extenuating circumstances outside of our control (e.g. pandemic). The determination to conduct the visit remotely will be made on a case-by-case basis to ensure patient safety and will not affect the integrity of the study data and outcomes.

7.2.1 Prescreen

Patients will be screened and recruited as outlined in Section 4, Recruitment Methods. If they meet outlined criteria they will be contacted by the study coordinator for Study visit 1 - Screening Visit.

During prescreening, the subject will confirm whether she is currently taking hormonal medication for contraception and/or endometriosis related issues. Depending on her current medication, she may need to delay enrollment into the study. If they are not already on NETA, they will need to consult with their primary physician in order to initiate the medication. Patients will also be advised to consult with their primary physician in order to determine whether they can initiate NETA and stop their current medication regiment. Once the patient is enrolled in the study, NETA will be provided by the IDS.

If the patient is not currently on NETA, they will need to be transitioned as follows:

- 1. None No delay
- 2. Combined oral contraceptive No delay
- 3. Etonogestrel/ethinyl estradiol vaginal ring No delay
- 4. GnRH antagonist (e.g. Orlissa) No delay
- 5. Long acting reversible contraception (Progesterone IUD, Copper IUD) No delay
- 6. GnRH agonist (e.g. Lupron Depot): 3.75 mg must wait 1 month from administration of prior injection and 11.25 mg- must wait 3 months from administration of prior injection.
- 7. Injectable Progesterone (Depo Provera) Must wait 3 months from administration of prior injection
- 8. Progestin-containing contraceptive implant Excluded from the studied

For women using methods listed #1-4, they will stop/remove this form of contraception and be transitioned immediately to NETA.

For women using LARCS listed #5, they can continue this form of contraception and be transitioned immediately to NETA.

For women using methods #6-7, they must wait the listed time prior to initiation of NETA.

All subjects will be required to be on NETA for 30 days prior to the enrollment visit.

The NETA is intended for the purposes of endometriosis related standard of care and is not considered an appropriate contraceptive method for patients. Acceptable methods of contraception are listed in Section 7.2.3.

We will confirm they are not currently taking any of the exclusionary medications/drugs in their described manners. If they have recently stopped the below products, their required washout period is listed below:

- 1. *Cannabis* based products (this will be further confirmed on toxicology testing at the screening visit) (required washout period: 30 days)
- Chronic daily use of drugs (≥ 10 days/month) that cause somnolence/sedation such as benzodiazepines or Central Nervous System (CNS) depressants (required washout: 30 days)
- 3. Clobazam (required washout period: 14 days)
- 4. Valproate (required washout period: 14 days)

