7.2.2 Study Visit 1: Screening Visit

Pre-screening will take place in the Penn State Hershey MIGS clinic or over the phone with women identified as potential candidates for study participation via prior clinic visits. If the subject meets all pre-screening criteria, she will return for a screening encounter and undergo informed consent prior to any study procedure. The subject will be given ample time to ask questions or voice concerns about the study.

A detailed history and physical exam will be performed, particularly to assess for concomitant use of anti-epileptic drugs and or underlying risk of liver dysfunction. We will need approximately 8-10 cc of blood (approximately 2 teaspoons).

- 1. Liver function tests (LFTs) will be drawn.
- 2. Baseline CBC and BMP will be drawn.
- 3. Screening urine toxicology will also be performed to confirm no recent THC use.
- 4. Urine pregnancy test will be collected.
- 5. Pain medication and narcotic usage from the prior month will be assessed.
- 6. Suicidal ideation will be assessed via the Columbia-Suicide Severity Rating Scale (C-SSRS).

If the subject is found to be pregnant, have evidence of underlying hematologic/ urologic/ hepatobiliary dysfunction or a positive urine toxicology for recent THC use, the subject will be excluded.

Current medication usage will be reviewed thoroughly with special attention paid to Cytochrome P450 (CYP) inducers and inhibitors as well as Substrates of uridine 5'-diphosphoglucuronosyltransferase (UGT). If the subject is screened into the study, their condition and corresponding medication will be recorded throughout the study. Please refer to Section 10 Risks, Drug Interactions, for additional guidelines.

Baseline survey data will be collected and entered into the RedCap secured database. This information will include the WERF EPHect Questionnaire.

At this time subjects will be set up for emails to complete VAS scores directly into RedCap. If not done already, the subject will be transitioned to norethindrone acetate to start taking immediately and given instruction on how to complete the VAS scores and study questions. It will be explained to the patient that she must complete 5 out of 7 days of surveys to be enrolled into the study. If the subject is unable to complete the 5 out of 7 days, the subject will be given one additional week to determine if compliance is attainable. If the subject is unable to do so, they will screen fail.

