7.2.3 Study Visit 2 – Enrollment Visit

The subject will be scheduled for a randomization/enrollment 1-2 weeks after the screening visit. The randomization will be double blind and 1:1:1. The patient will have been expected to be on norethindrone acetate (NETA) for 30 days prior to the enrollment visit. Dosing for norethindrone acetate will start at 5mg oral daily, but may be adjusted from 2.5 mg to 15 mg depending on the subject's needs to achieve amenorrhea as this standard treatment for endometriosis or to increase compliance by reducing side effects. The study team will be responsible for adjusting dosages at subsequent study visits 3 and 4. At this visit, the subject will be randomized into Group A, Group B, Group C by IDS as long as the subject has met all the criteria for enrollment. The groups are listed below:

Group	Treatment
А	Norethindrone acetate + Placebo (Hemp Seed Oil)
В	Norethindrone acetate + low dose CBD (10mg sublingual daily)
С	Norethindrone acetate + high dose CBD (20mg sublingual daily)

The subject will be given a 4 week supply of (1) placebo (2) low dose CBD or (3) high dose CBD product and instructed on its application. The subject will also receive a 4 week supply of norethindrone. Refer to the following:

- a. In the morning, take the norethindrone acetate orally with a sip of water at approximately the same time each day. This can be taken on an empty or full stomach.
- b. Prior to bed, you will administer the study drug.
 - 1. Please refrain from eating (drinking is permissible) 60 minutes prior to administration.
 - 2. Place 4 drops of the study drug under your tongue.
 - 3. Hold the study drug under the tongue for 60 seconds. After that time, swallow any remaining drug.
 - 4. Repeat steps 2 and 3 for a total of 8 drops.

Please avoid eating, drinking or smoking for 2 hours after administration.

A focus group was conducted to determine the optimal route of administration of the study drug. 1 application of 8 drops of the study drug versus 2 applications of 4 drops were compared and it was determined that the latter method was preferred.

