7.3 Duration of Participation

Study participation is expected to be 13-14 weeks. For those who participate in the optional PK study, participation may extend to 12-24 weeks post-enrollment.

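### A woman who starts NETA at Visit 1 cannot have the required 30 days of NETA by Visit 2, which is set 1-2 weeks later

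*Combined protocol and SAP*

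**What the plan says.** The lead-in rule appears twice. Section 7.2.1: "All subjects will be required to be on NETA for 30 days prior to the enrollment visit". Section 7.2.3: "The patient will have been expected to be on norethindrone acetate (NETA) for 30 days prior to the enrollment visit".

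Section 7.2.2 provides for a woman who reaches Visit 1 without NETA: "If not done already, the subject will be transitioned to norethindrone acetate to start taking immediately".

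The gap to randomisation is also given twice. Section 7.1: "After the screening visit, the subjects will be scheduled to have a 1-2 week follow-up for the enrollment visit". Section 7.2.3: "The subject will be scheduled for a randomization/enrollment 1-2 weeks after the screening visit". Sections 7.1 and 7.2.2 allow one further week, but only for poor diary completion.

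Section 7.3 gives the total: "Study participation is expected to be 13-14 weeks".

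Two other texts bear on timing. In Section 7.2.1, women not on NETA are sent to their own doctor at prescreening: "they will need to consult with their primary physician in order to initiate the medication". The same section says that, depending on current hormonal medication, "she may need to delay enrollment into the study". The waits it then lists (GnRH agonist, injectable progesterone) run before NETA is started. The other permitted methods carry no wait.

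Section 7.2.3 allows randomisation only for women who satisfy the enrolment criteria. The numbered inclusion criteria in Section 3.1 require agreement to move to NETA or add it. They do not include 30 days of it.

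**The concern.** For a woman who first takes NETA at Visit 1, the start date, the interval and the lead-in rule conflict. The site has to break one of them, and the protocol does not say which.

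If the interval is kept, her baseline surveys, VAS and inflammatory markers at Visit 2 are taken early in a new hormonal treatment. Section 8.3 compares the secondary endpoints as change from that baseline. The primary endpoint is the VAS area under the curve (AUC) over the 8 weeks after randomisation, so part of her early response to NETA could fall inside it. If the lead-in is kept instead, the visit interval and the stated duration no longer hold for her.

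**Working it through.** This is calendar arithmetic.

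Inputs:
- Required NETA before Visit 2: 30 days (Sections 7.2.1 and 7.2.3)
- Latest NETA start provided for: the day of Visit 1 (Section 7.2.2)
- Visit 1 to Visit 2: 1-2 weeks = 7-14 days (Sections 7.1 and 7.2.3)
- Extra diary period: 7 days, once, for poor adherence only (Sections 7.1 and 7.2.2)
- Visit 2 to Visit 4: 8 weeks = 56 days; Visit 2 to Visit 5: 12 weeks = 84 days (Section 7.1)

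1. **The plan's own duration.** Participation = (Visit 1 to Visit 2) + 84 days. This gives 7 + 84 = 91 days = 13 weeks, and 14 + 84 = 98 days = 14 weeks. It matches Section 7.3 exactly, so the stated duration assumes the 1-2 week gap and has no room for a 30-day lead-in after Visit 1.

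2. **NETA at Visit 2 for a Visit 1 starter.** Days on NETA equal the gap: 7-14. Shortfall: 30 - 14 = 16 to 30 - 7 = 23 days.

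3. **With the extra diary week on top.** 7 + 7 = 14 to 14 + 7 = 21 days. Shortfall: 30 - 21 = 9 to 30 - 14 = 16 days. No scheduled path from a Visit 1 start reaches 30.

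4. **If the interval is kept.** Day 30 of NETA comes 16-23 days after randomisation. As a share of the AUC window this is 16/56 = 28.6% to 23/56 = 41.1%.

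5. **If the 30-day rule is kept.** Visit 2 falls at least 30 days after Visit 1. Participation is then at least 30 + 84 = 114 days, and 114/7 = 16.3 weeks, against 13-14.

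6. **If both are kept.** NETA must start 16-23 days before Visit 1, which is the prescreening route and not the Visit 1 start.

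**The case against.** The strongest reply is that the protocol already handles this. The planned route is a start through the woman's own doctor at prescreening. The delay sentence in Section 7.2.1 can be read as moving Visit 2, which is called the enrolment visit. The rule covers all subjects, and randomisation depends on the criteria being met. Section 7.4.2 allows NETA for up to 12 weeks alongside 8 weeks of study drug, which is close to 30 + 56 = 86 days (12.3 weeks) and suggests that a lead-in of about a month was intended.

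Much of this stands. The prescreening route is consistent: a woman who started NETA early enough meets every rule. A reader might infer that this route is itself a fault because NETA begins before written consent. The documents do not support that, since they present NETA as standard care begun with the woman's own doctor.

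A reader might also infer that Visit 1 starters will in fact be randomised after 7-14 days. That is possible but not established. The natural reading of a rule stated twice is that such a woman waits. The gate is not secure, though, because Section 3.1 omits the rule and a coordinator checking that list could randomise her in good faith.

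The reply does not remove the conflict. Section 7.2.2 expressly provides for women who arrive without NETA. The only waits that Section 7.2.1 specifies come before NETA starts, and no text lengthens the gap to Visit 2. The 12-week allowance does not settle the matter either, because the study period it refers to is not defined.

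**Conclusion.** The point holds as a minor scheduling error. For a woman who starts NETA at Visit 1, the start, the 1-2 week interval and the 30-day rule cannot all be followed. The shortfall is 16-23 days on the written schedule, and 9-16 days if the extra diary week is added on top. Enforcing the rule instead takes her to about 16 weeks.

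The effect on endpoints is conditional. The 29-41% of AUC days before day 30 of NETA arises only if the rule is breached. The documents give no NETA response curve and no reason to treat day 30 as the point of stability. Section 7.2.3 also lets the NETA dose vary from 2.5 to 15 mg, with adjustment at later visits, so exposure can change within the window even for compliant women. Any added noise in a pilot of 36 therefore cannot be sized.

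A reader might infer a biased treatment comparison. Nothing shows one: every arm receives NETA and allocation is randomised. The number of women who would start at Visit 1 is not given.

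**What to change.** - In Sections 7.1 and 7.2.3, state that Visit 2 takes place 1-2 weeks after Visit 1 or at least 30 days after NETA start, whichever is later.
- Add 30 days of NETA to the criteria in Section 3.1 that are checked before randomisation.
- For Visit 1 starters, take the 7-day diary run-in in the last 1-2 weeks before Visit 2. With Visit 2 on day 30, the run-in fits on days 16-22 and the one extra week on days 23-29.
- In Section 7.3, give about 16 weeks for these women.

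The physician-led start at prescreening stays as planned.

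The cost is a protocol and consent-form amendment and 16-23 more days of screening for Visit 1 starters. They would need about a month of NETA before Visit 2, while Section 7.2.1 has the investigational pharmacy supply it only once a woman is enrolled, so the amendment should say who provides it. No extra randomised patients are needed, and nothing changes for women who will already have 30 days of NETA by Visit 2.
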